#### ***Rationale for biomarkers***

NFL is a biomarker correlated with prognosis and remain relatively stable over time. A change in the expression of NFL may, therefore, be considered as a potential disease amelioration in ALS (Verber et al., 2019). Plasma creatinine is a surrogate ALS biomarker of muscle mass and is decreased in ALS patients. Serum creatine kinase (CK) is increased in ALS patients and correlates with survival in some studies. Both are considered muscle denervation biomarkers in ALS. Urinary P75ECD is a surrogate ALS biomarker and is elevated in ALS patients. The three biomarkers are associated with disease progression (Verber et al., 2019). To measure the pharmacological effect (target engagement) of edaravone, oxidative stress biomarkers, like 8-OHdG, will be measured (Verber et al., 2019).

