**\* Only labs parameters that are abnormal in the screening visit will be re-evaluated in baseline visit.**

- Urine samples for urinalysis
- Urine pregnancy test only in women of childbearing potential
- Plasma vitamin B6 levels, and, if necessary, vitamin B6 supplements (pyridoxine (100 mg/day)) will be prescribed.
- ALS evaluation procedures: ALSFRS-R, Slow Vital Capacity (SVC), Hand-Held Dynamometry, ALSAQ-40, Edinburgh Cognitive and Behavioural ALS Screen (ECAS), EQ-5D-5L, VAS, King's staging system and MiToS.
- Blood sampling for biomarker: neurofilament light (NFL). Creatinine and creatine kinase will be measured in routine biochemistry lab testing.
- Urine collection for biomarkers: urinary extracellular domain of neurotrophin receptor p75 (Urinary P75ECD) and oxidative stress biomarker 8-hydroxyguanosine (8-OHdG)
- Blood sampling for genotyping for Future Biomedical Research (FBR) (if consented)

- Blood sampling for RNA and serum collection for FBR (if consented)
- Cerebrospinal fluid (CSF) sampling for Future Biomedical Research (if consented)
- Dispensing study Medication: Instructions for dosing FAB122 and first dosing
- Blood sampling for FAB122, in selected sites if consented. Specific ICF will be provided.
- Blood sampling for riluzole, in selected sites if consented. Specific ICF will be provided.
- Adverse Events monitoring
- Cost questionnaire

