### 11.2. Sample Size Determination

The sample size estimation is based on the primary endpoint: the change from baseline in ALSFRS-R score after 48 weeks. A difference of 3.0 points between FAB122 treatment arm and placebo is assumed with a (pooled) standard deviation of 7.5 and an allocation ratio of 2:1 (FAB122:Placebo). With these assumptions, a total sample size of 300 (200 patients on FAB122 and 100 on placebo) is needed to achieve 90% power to detect the difference of 3.0 points between the two treatment groups at a 5% (2-sided) level of significance.

The standard deviation of 7.5 is based on recent study results with edaravone using a similar trial population as applied in this trial, where standard deviations varied between 3.4 and 6.9 (The Writing Group on behalf of the Edaravone (MCI-186) ALS 19 Study Group. 2017 b, 2017;). The variability in this study can be expected to be somewhat higher due to the change of formulation and due to the fact that in this study patient can use riluzole as background therapy.

The hypothesis in this study includes detection of a difference of 3 points in ALSFRS-R at week 48 between the two treatment arms. The patients in the placebo group in ALS studies typically deteriorate by 1 point per month, so 12 points in 12 months. A difference of 3 points therefore corresponds to a 25% difference in deterioration, which is considered clinically significant.

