### **5.6.1 Primary analysis**

The primary endpoint is defined as the change from baseline in total ALSFRS-R score after 48 weeks (primary timepoint).

For the primary analyses, a placebo (reference) multiple imputation (pMI) will be applied to impute missing data for any patients (i.e. from both treatment arms) who discontinue treatment early, irrespective the reason for drop-out (only when due to intercurrent events with unknown cause), and for which no data was collected after treatment discontinuation. The pMI method assumes the statistical behavior of placebo- and drug-treated patients after dropout is the statistical behavior of placebo-treated patients. A total of 20 imputed data sets will be created.

Before applying the statistical model to the primary endpoint, intercurrent events will be handled following the rules specified in Section 5.2.

The primary endpoint will be analyzed using a mixed model for repeated measures (MMRM), considering ALSFRS-R is assessed at multiple timepoints. The average treatment effect (lsmeans) and the treatment difference (estimand) of the change from baseline ALSFRS-R total score at 48 weeks will be extracted from the results from this model and presented together with the 95% confidence interval and p-value. Other timepoints will also be presented.

The model will include factors for treatment, time, treatment-by-time interaction, the stratification factor concomitant use of riluzole (yes/no), baseline ALSFRS-R score and the stratification factor slope of disease progression as fixed effects. An unstructured (UN) covariance matrix will be used in the model. If the model does not converge, the structure will be adapted to respectively AR(1), Toeplitz or Compound Symmetry (CS). The results of the 20 imputed data sets will be combined to obtain the final estimate of the treatment difference with 95% confidence interval and p-value.

An example SAS code which can be used as basis is as follows:

```
proc mixed data=<data>;
  class trt time riluse;
  model cfb=trt time trt*time riluse base disslope / ddfm=kr;
  repeated time/ subject=patient type=un;
  lsmeans trt*time/cl;
run;
```

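### The primary MMRM leaves out baseline neurofilament light, a prognostic value the trial already collects; adding it before unblinding is a cheap gain in precision, not the repair of an error

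*SAP*

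**What the plan says.** SAP section 5.6.1 lists the model terms: "The model will include factors for treatment, time, treatment-by-time interaction, the stratification factor concomitant use of riluzole (yes/no), baseline ALSFRS-R score", together with the slope of disease progression. The example SAS code has the same terms. Protocol sections 11.3.4.2 and 11.4 name the same covariates. NFL appears in none of these places.

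On NFL itself, the protocol's rationale for biomarkers says: "NFL is a biomarker correlated with prognosis and remain relatively stable over time". Protocol section 3.2.4 labels NFL prognostic in the list of exploratory endpoints. The Visit 1 list in protocol section 6.2 includes an NFL blood sample for everyone. The future-research, CSF and PK samples in that list depend on consent or selected sites; the NFL sample does not. First dosing comes later in the same list, and SAP section 5.1 defines baseline as the last value before the first dose.

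The only use the SAP specifies for NFL is the exploratory summary by arm in section 5.6.4, which already plans a natural-log scale. In SAP section 5.2, the as-treatment imputation allows further covariates but names none. Neither document gives a reason for leaving NFL out of the model.

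**The concern.** A baseline variable that predicts the outcome leaves variance in the week-48 contrast when it is not modelled, and randomisation balances it only on average. Adjusting for it removes that part of the noise and corrects for chance imbalance between arms. Here the variable is scheduled for every patient, so no new visit or sample is needed.

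The primary endpoint is the first step of the fixed testing sequence in SAP section 4.1. Precision on it therefore also decides whether CAFS and survival time can be tested as confirmatory.

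**Working it through.** **1. Reproduce the plan's figure.** Inputs from protocol section 11.2: difference 3.0, SD 7.5, allocation 200:100, two-sided 5%, 90% power.

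- Placebo n = (1.960 + 1.282)² × 7.5² × (1 + 1/2) / 3.0² = 98.5, rounded up to 99. With 198 on FAB122 the total is 297, against a stated 300.
- Standard error at 200:100 = 7.5 × √(1/200 + 1/100) = 0.919. Noncentral-t power on 298 degrees of freedom is 90.2% (normal approximation 90.4%).

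The stated design reproduces. The protocol mentions no covariate credit in the SD of 7.5.

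**2. Relative gain in precision.** Let R² be the share of the week-48 variance *left after the planned covariates* that log baseline NFL explains. The standard error is multiplied by √(1 − R²), whatever the starting SD. The equivalent sample size is 300/(1 − R²). The R² values are assumptions, because the documents give none.

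| Assumed R² | Fall in SE | Equivalent N |
|---|---|---|
| 0.05 | 1 − √0.95 = 2.5% | 316 |
| 0.10 | 1 − √0.90 = 5.1% | 333 |
| 0.15 | 1 − √0.85 = 7.8% | 353 |

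**3. Gain in power.** This depends on the share b that the planned covariates already explain, also an assumption. Residual SD = 7.5 × √((1 − b)(1 − R²)). With R² = 0.10:

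| Assumed b | SD without NFL | Power | SD with NFL | Power |
|---|---|---|---|---|
| 0 | 7.50 | 90.2% | 7.12 | 92.9% |
| 0.20 | 6.71 | 95.3% | 6.36 | 97.0% |
| 0.30 | 6.27 | 97.3% | 5.95 | 98.4% |

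On unrounded figures the gains are about 2.7, 1.6 and 1.1 percentage points. The first row also applies if 7.5 was meant as a residual SD, which the protocol does not say. Starting instead from 6.9, the top of the range the protocol cites ("where standard deviations varied between 3.4 and 6.9"), power goes from 94.3% to 96.2%.

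In the first row the 95% confidence interval half-width goes from 1.96 × 0.919 = 1.80 to 1.96 × 0.871 = 1.71 points.

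**4. Missing baseline NFL.** If patients without a value were dropped, a missing fraction m would change the variance by the factor (1 − R²)/(1 − m). The gain is cancelled when m = R²: 5% missing wipes out an R² of 0.05. A rule that keeps every patient is therefore essential.

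These figures treat the week-48 comparison as a simple two-sample contrast. They ignore the reference-based imputation and the worst-percentile handling of deaths in SAP section 5.2.

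**The case against.** **It is a preference, not a defect.** The model adjusts for both stratification factors and baseline score, agrees with the protocol on covariates, and is valid. This stands. A reader might infer that omitting NFL biases the result or leaves the trial underpowered. The documents support neither, since the sample size reproduces with no covariate credit.

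**The gain may be small.** Slope is already in the model, and eligibility restricts progression to 0.35–1.5 points per month, onset to 24 months and SVC to at least 70% of predicted. The protocol links NFL to prognosis; it does not say that NFL predicts ALSFRS-R change given slope and baseline score. This stands, and it is why only a range can be given. How much is left for NFL also depends on how slope enters. The SAP text calls slope a stratification factor, which is a split at 1.0, but the example code does not declare it as a class variable.

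**Why NFL alone?** The protocol also associates creatinine, creatine kinase and urinary p75 with progression, and SVC is measured at baseline. However, NFL is the biomarker that the protocol's endpoint list singles out as prognostic, which is a reasonable basis for one prespecified covariate.

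**Some facts are inferred.** A reader might take it as stated that NFL is drawn before the first dose and that few values will be missing. The first rests on the order of the Visit 1 list and the SAP's baseline definition. Neither document gives expected NFL completeness. Both need checking.

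**The change is not confined to one SAP sentence.** It departs from the protocol model, and the SAP is already at final version 4.0. This stands as a cost. SAP section 1 still places finalisation before database lock and unblinding.

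**Conclusion.** The point holds as a missed gain in precision. The planned primary analysis remains valid and the 90% power claim is sound on its own inputs.

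The relative fall in standard error, 2.5 to 7.8%, rests only on the assumption that NFL explains a further 5 to 15% of the variance left by the planned covariates. The power gain needs a second assumption, about what those covariates already explain. For a further 10% it is roughly 1 to 3 percentage points. It may be near zero if slope and baseline score already carry the NFL information.

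A reader might apply the 5 to 15% directly to the SD of 7.5 and quote a rise from 90.2% to as much as 94.2%. That holds only if the planned covariates explain nothing, or if 7.5 is already a residual SD; the documents establish neither. The case for the change is its low cost, not a large or certain benefit.

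**What to change.** Before unblinding, amend the SAP as follows:

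- **Model.** Add log-transformed baseline NFL and its interaction with visit to the primary MMRM in section 5.6.1, and add log baseline NFL to the imputation model.
- **Timing.** Use only samples confirmed as taken before the first dose.
- **Missing values.** Replace missing baseline NFL with the pooled baseline mean on the log scale, blind to arm, so that no patient is dropped.
- **Sensitivity analysis.** Keep the current model without NFL.
- **Record.** List the departure from protocol sections 11.3.4.2 and 11.4 in SAP section 6.
- **Scope.** State whether NFL also enters the CAFS ANCOVA and the secondary models described as similar to the primary one. CAFS is affected in any case, because it uses week-48 scores imputed under section 5.6.1.

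Cost: SAP wording and programming, with no new patients, visits or samples. Baseline NFL results must be in the database before lock. The interaction means one NFL coefficient per visit, up to 12 by week 48, a small loss of degrees of freedom with about 300 patients.

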##### **11.3.4.2. Primary Efficacy Endpoint**

The primary endpoint is defined as the change from baseline in ALSFRS-R score after 48 weeks (primary time point).

For the primary analyses placebo (reference) multiple imputation will be applied to impute missing data for any subjects (i.e. from both treatment arms) who discontinue treatment early, irrespective the reason for drop-out, and for which no data was collected after treatment discontinuation. A total of 20 imputed data sets will be created.

Linear mixed modelling for repeated measures will be applied on each of the imputed data set to estimate the average (lsmeans) treatment effects and the treatment difference (estimand) of the change from baseline of ALSFRS-S score at week 48.

The model will include factors for treatment, time, treatment-by-time interaction, and concomitant use of riluzole (yes/no) as fixed effects and baseline ALSFRS-R score and slope of disease progression (based on change in ALSFRS-R score) as (random) covariates.

The results of the 20 imputed data sets will be combined to obtain the final estimate of the treatment difference with 95% confidence interval and p-value.

The primary analysis will be performed on the modified intent-to-treat population (mITTs), i.e. all randomized patients who had at least one treatment intake

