### 5.5.3 Baseline characteristics

The patient baseline characteristic “substance use” and the stratification groups (the slope ALSFS-R score from the time of first symptoms until screening, concomitant use of riluzole) will be summarized per treatment group and overall using the safety population. Baseline characteristics will also be listed.

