#### **Combined assessment of function and survival (CAFS) at week 48 and 72**

CAFS is used to compare each study patient's outcome to others in the trial in a series of pairwise comparisons, based on function (i.e. ALSFRS-R score) and survival. See section 9.1 for relevant derivations. For each pairwise comparison, a study patient is assigned a score and then the summed scores are ranked for all patients.

Descriptive statistics for CAFS ranks will be made but are difficult to interpret as mean values depend on the size of the study. Descriptive statistics will also include mean difference in ranks with a 95% CI.

The difference between treatments CAFS ranks will be assessed using the Gehan-Wilcoxon rank test (also known as the Generalized Wilcoxon test) or, in case of relevant differences in baseline characteristics (as per factors included in the ANCOVA model mentioned), by using an ANCOVA model.

Regarding the Gehan-Wilcoxon rank test: if the analysis indicates a statistically significant effect, then the separate analysis of function and survival (as described below in the other secondary endpoints section) can provide insight whether the improved outcome for the group was driven by prolonged survival, improved function, or both. In case of an ANCOVA model: a General Linear Model (GLM) will be utilized with treatment, baseline ALSFRS-R score and stratification factors (slope of disease progression, concomitant use of riluzole) as covariates.

ALSFRS-R score values for patients who survived but have a missing week 48 score will be imputed following to the imputation defined in section 5.6.1, before the CAFS score will be

determined. The GLM will omit any (other) patients with missing data from the analysis. The duration from symptom onset is calculated from the medical history data.

In case of GLM, subsequent component analyses of function and survival will be used to determine which parameter(s) drive the overall effect on the CAFS results. The direction and magnitude of the function and survival components of the CAFS will inform the interpretation of the results.

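### The primary model gives pre-study slope a single coefficient for all visits; if slope is prognostic and its effect grows roughly in proportion to time, the week-48 standard error is too wide and a little power is forgone

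*SAP*

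**What the plan says.** SAP section 5.6.1 lists treatment, time, treatment-by-time, riluzole use, "baseline ALSFRS-R score and the stratification factor slope of disease progression as fixed effects". The example code has the same terms: "model cfb=trt time trt*time riluse base disslope / ddfm=kr". For the covariance, "An unstructured (UN) covariance matrix will be used in the model", with AR(1), Toeplitz or compound symmetry if the model fails to converge. The same section applies this model in the sensitivity analyses. Protocol sections 11.3.4.2 and 11.4 also list slope without an interaction with time.

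Protocol section 4 stratifies the 2:1 randomization by slope from first symptoms to screening (below 1.0 versus 1.0 or more) and by riluzole. Entry criterion 5 in Protocol section 5.2 limits that slope to 0.35-1.5 points per month. The sample size (Protocol section 11.2, SAP section 2.4) uses a 3.0-point difference and SD 7.5, and takes no credit for covariate adjustment.

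**The concern.** Pre-study slope is a rate in points per month, and Protocol section 11.2 expects decline to build up at about 1 point per month. Any effect of slope on change from baseline should therefore be small at week 4 and largest at week 48. A single coefficient has to compromise across visits. Under an unstructured covariance the early, low-variance visits carry most of the weight, so the fitted coefficient is far below the week-48 effect. The unstructured matrix does not stand in for the missing interaction: it counts the unmodelled slope effect as residual variance at week 48. What is at stake is precision at the primary time point, from a covariate that is already collected for eligibility and stratification.

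**Working it through.** **1. The plan's own figure.** SE = √(7.5² × (1/200 + 1/100)) = √(56.25 × 0.015) = 0.919. Power = Φ(3/0.919 − 1.96) = 90.4%, and 297 patients would be enough. The stated 300 for 90% power is reproduced.

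**2. Plausible correlation r between slope and week-48 change.** The documents give none. A uniform slope over 0.35-1.5 (assumed shape) has SD 1.15/√12 = 0.332 per month. If past slope carried forward in full over 48 weeks (11.04 months), r = 0.332 × 11.04 / 7.5 = 0.49. Correlations of 0.2, 0.3 and 0.4 need 41%, 61% and 82% carry-over, so 0.4 is near the top.

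**3. What a single coefficient keeps.** Let b be the vector of true slope effects by visit, S₀ the residual covariance given slope (slope scaled to SD 1), and **1** a vector of ones. The common coefficient g solves g = **1**′S⁻¹b / **1**′S⁻¹**1** with S = S₀ + (b − g**1**)(b − g**1**)′. The share of week-48 variance reduction kept is 1 − (1 − g/b₄₈)².

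Base case: the 12 scheduled ALSFRS-R assessments from week 4 to week 48 (Protocol section 8.1.1), effect linear in time, random-slope residual, and error SD 1.5 (assumed). For r = 0.1-0.4, g/b₄₈ = 0.023-0.027, so about 5% is kept. Other cases:

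- Other random-slope and random-walk residuals, linear growth, 12 visits: 2-27%.
- Five clinic visits only, base-case residual: about 8%.
- Growth as t^0.7: about 30-46%. Growth as √t: about 55%.
- Fallback AR(1), Toeplitz or compound symmetry: about 79%.

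**4. Allow for stratified randomization.** With uniform slope, the share below 1.0 is 0.65/1.15 = 0.565. Within-stratum variance is 0.565 × 0.65²/12 + 0.435 × 0.50²/12 = 0.0290, against a total of 1.15²/12 = 0.1102. The ratio is 0.263, so stratification removes about 74% of chance imbalance in slope between the arms. The planned model's SE does not reflect this.

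**5. Week 48 at r = 0.4.** Residual variance given slope = 56.25 × (1 − 0.16) = 47.25; slope part = 9.00. The planned model leaves (1 − 0.027)² × 9.00 = 8.52 of it.

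- Planned model SE = √((47.25 + 8.52) × 0.015) = 0.915.
- Planned actual SE = √((47.25 + 0.263 × 8.52) × 0.015) = 0.862.
- Planned power = Φ((3 − 1.96 × 0.915)/0.862) = 91.9%. Type I error = 2Φ(−1.96 × 0.915/0.862) = 3.8%.
- Stratum × time: SE = √((47.25 + 0.263 × 9.00) × 0.015) = 0.863, power 93.5%.
- Continuous slope × time: SE = √(47.25 × 0.015) = 0.842, power 94.6%.

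The same formulas at each correlation give:

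| r | Planned model SE | Planned actual SE | SE, continuous × time | Power: planned | Power: stratum × time | Power: continuous × time |
|---|---|---|---|---|---|---|
| 0.2 | 0.918 | 0.905 | 0.900 | 90.8% | 91.2% | 91.5% |
| 0.3 | 0.917 | 0.887 | 0.876 | 91.3% | 92.2% | 92.8% |
| 0.4 | 0.915 | 0.862 | 0.842 | 91.9% | 93.5% | 94.6% |

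**6. Check by simulation.** Week 48, blocked 2:1 allocation within stratum, 12,000 trials per correlation: power went from 90.4% to 91.1%, from 90.7% to 92.5% and from 91.7% to 94.4% with continuous slope. At r = 0.4 the planned model SE was 0.914 and the actual SE 0.859. A second simulation at r = 0.4 gave 0.915 and 0.863, type I error about 4%, and power 91.7% planned, 93.2% with the stratum and 94.2% with continuous slope.

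**7. Deaths.** With 15% deaths (assumed; SAP section 5.2 expects under 17%) set to worst-5% values, adding slope × time cut the SE from 0.976 to 0.965, 0.974 to 0.947 and 0.974 to 0.923 at r = 0.2, 0.3 and 0.4. These are reductions of 1.1%, 2.8% and 5.2%. The corresponding reductions in model SE with complete data are 2.0%, 4.5% and 8.0%. Neither set allows for stratified allocation, so only the direction should be read from them. Placebo-based imputation was not simulated.

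**The case against.** The strongest objection is that this is a refinement and not an error. Protocol and SAP agree on a main-effects covariate model, the stated power does not rely on any covariate gain, and the two inputs that decide the size (the correlation and the growth shape) are not in the documents. All of that stands. It limits the point to a minor, conditional one. It does not remove it, because the added term costs almost nothing if slope turns out not to be prognostic.

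Three stronger readings are tempting, and the documents do not support them.

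- **A large loss of sample size.** Comparing model SEs at r = 0.4 gives (0.915/0.842)² = 1.18, or 18% more patients. That ignores the stratification in Protocol section 4. On actual SEs the ratio is (0.862/0.842)² = 1.05. Most of the difference is over-wide reporting.
- **Bias or an underpowered trial.** Simulated estimates stayed close to the true value under every model, and planned power is at or above 90% with complete data under the stated assumptions.
- **A conflict over the form of slope.** The code has "class trt time riluse" and so leaves slope out, while the protocol has "baseline ALSFRS-R score and slope of disease progression (based on change in ALSFRS-R score) as (random) covariates". A reader might infer an unrecorded switch from a continuous covariate to a stratum. The protocol phrase describes the stratum equally well, the SAP names the stratum consistently (also for CAFS: "stratification factors (slope of disease progression, concomitant use of riluzole) as covariates"), and a 0/1 stratum fits the same with or without the CLASS statement. This is at most a missing definition.

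**Conclusion.** The point holds as a minor, free improvement. The conclusion that little is kept depends on the planned unstructured matrix and on an effect growing roughly in proportion to time; slower growth or a fallback structure keeps much more. Because of stratified allocation, the main consequence is a confidence interval that is too wide and a test that is slightly conservative, with a smaller real loss from slope differences within strata. The gains of about 1, 2 and 2.5-3 percentage points of power also assume uniform slope and complete data, and they shrink with deaths.

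**What to change.** Before unblinding, add disslope*time to the primary model and to the sensitivity analyses that reuse it, and record the change in SAP section 6 as a departure from Protocol sections 11.3.4.2 and 11.4.

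The minimal version crosses the stratum already named in the SAP with time. It corrects the SE and gives about half or more of the power gain (at r = 0.4, 1.5 of 2.5 points in simulation). Using the continuous screening slope crossed with time gives the rest. State in one line which form disslope takes. A baseline-by-time term is optional, and no gain is claimed for it.

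The cost is up to 11 fixed-effect degrees of freedom with 12 visits (4 with five clinic visits) among 300 patients, and no new data. If slope is not prognostic, the simulated SE rises from 0.916 to 0.918, equivalent to about 0.3% of patients.

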The primary strategy for handling the IE will consist of the "Treatment Policy" strategy applied for all these intercurrent events, i.e., the efficacy observed assessment will be used regardless of the intercurrent event. Therefore, overall the amount of missing data generated will be a very small. For these cases a placebo (copy from reference) multiple imputation will applied. A total of 20 imputed data sets will be created.

However, it is noted that the "Treatment Policy" strategy will not be applicable for terminal intercurrent events such as death (IE #g) or when there are real lost to follow-up cases after doing all efforts to retrieve the data (some cases in IE #f). For cases with missing data in IE #f, the same general approach as described above will be implemented. For related death (IE #g) it is proposed to use a "Composite strategy" and thus a conservative scenario using a 95th worst percentile combined with multiple to avoid variance artefactual shrinking.

---

- h. Population-level summary: the change from baseline in ALSFRS-R score after 48 weeks (primary time point), using a linear mixed modelling for repeated measures. The model will include factors for treatment, time, treatment-by-time interaction, and concomitant use of riluzole (yes/no) as fixed effects and baseline ALSFRS-R score and slope of disease progression (based on change in ALSFRS-R score) as (random) covariates (see section 11.3.4.1)).

To evaluate the impact of missing data and of the handling methods, a number of sensitivity analyses will be performed for the primary endpoint:

- **As treatment multiple imputation:** For any subject with missing values, the estimates for the missing assessments will be based on the actual treatment group of that subject. One hundred imputations will be performed.

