## 2.4 Sample size

The sample size estimation is based on the primary endpoint: the change from baseline in ALSFRS-R score after 48 weeks. A difference of 3.0 points between FAB122 treatment arm and placebo is assumed with a (pooled) standard deviation of 7.5 and an allocation ratio of 2:1 (FAB122:Placebo). With these assumptions, a total sample size of 300 (200 patients on FAB122 and 100 on placebo) is needed to achieve 90% power to detect the difference of 3.0 points between the two treatment groups at a 5% (2-sided) level of significance.

For further details on the background of these assumptions, refer to the protocol.

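### If the unstructured MMRM fails to converge, SAP 5.6.1 falls back to equal-variance structures without robust standard errors; the week-48 test is then too liberal if variance grows over time (minor, cheap to fix)

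*SAP*

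**What the plan says.** SAP 5.6.1 (Primary analysis) specifies an MMRM for change from baseline in ALSFRS-R, fitted to each of 20 imputed data sets and combined. The covariance is unstructured, with this fallback: "If the model does not converge, the structure will be adapted to respectively AR(1), Toeplitz or Compound Symmetry (CS"). No heterogeneous-variance version of these structures is named.

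The example code contains "model cfb=trt time trt*time riluse base disslope / ddfm=kr" and no EMPIRICAL option. No other section of the SAP asks for robust standard errors. The code is offered as a basis and shows only the unstructured case, so the standard-error method for the fallback is never stated separately.

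Two Protocol statements bear on relevance and size. On missing data under the treatment-policy strategy, Protocol 11.4 expects that "overall the amount of missing data generated will be a very small". On variability, Protocol 11.2 plans with an SD of 7.5 and cites earlier edaravone results "where standard deviations varied between 3.4 and 6.9", without saying whether that range runs across visits.

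**The concern.** AR(1), Toeplitz and compound symmetry fit a single variance to all post-baseline visits. If the true variance rises over time, the fitted value is roughly an average over visits and lies below the week-48 variance. The standard error of the week-48 contrast is then too small. Kenward-Roger allows for having estimated the covariance parameters; it does not repair a structure that is wrong.

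Rising variance is plausible here. Protocol 5.2 admits patients who progress at 0.35 to 1.5 points per month. If those rates persisted, decline would range from about 0.3 to 1.4 points at week 4 (0.92 months) and from about 3.9 to 16.6 points at week 48 (11.0 months). The model includes the progression slope only as a main effect, with no slope-by-time term, so it does not remove this spreading.

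At stake is the confirmatory p-value, which also decides whether CAFS and survival time are tested as confirmatory under SAP 4.1. The error would favour the experimental arm's claim.

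**Working it through.** **Inputs.** From SAP 2.4: "A difference of 3.0 points between FAB122 treatment arm and placebo is assumed with a (pooled) standard deviation of 7.5"; "a total sample size of 300 (200 patients on FAB122 and 100 on placebo) is needed to achieve 90% power"; "at a 5% (2-sided) level of significance". From Protocol 8.1.1: ALSFRS-R at 12 post-baseline times to week 48 (five clinic visits and seven calls), hence 12 × 13 / 2 = 78 unstructured covariance parameters. Assumed, because the documents do not give it: how the SD changes from week 4 to week 48.

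**Plan's own figure.** SE = 7.5 × √(1/200 + 1/100) = 0.919. Power = Φ(3.0/0.919 − 1.96) = Φ(1.306) = 90.4%. The stated 90% is reproduced.

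**Complete data.** The week-48 estimate is essentially the same under any of these structures; only its SE changes. Let r = fitted SD / 7.5. Then type I error = 2 × [1 − Φ(1.96 r)].

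Compound symmetry can be checked by hand, because its fitted variance is the mean of the visit variances. For an SD rising linearly from 5 to 7.5 over 12 visits, the step is 2.5/11 = 0.227. The mean variance is 6.25² + 0.227² × (12² − 1)/12 = 39.06 + 0.62 = 39.68, so the fitted SD is 6.30, r = 0.840 and 1.96 r = 1.646. Type I error is 10.0%.

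For AR(1), the best-fitting (minimum Gaussian discrepancy) structure was found numerically. The 4-week correlation was 0.90 to 0.98 in the linear-SD rows, and the residual SD was 1, 2 or 3 in the first two rows:

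| Assumed growth to SD 7.5 | AR(1) SE at week 48 | Type I error |
|---|---|---|
| Strong: random slopes plus residual | 0.62-0.64 | 17.1-18.7% |
| Strong: variance linear in time plus residual | 0.68-0.72 | 12.4-14.6% |
| Strong: week-4 SD 3.4 | 0.70-0.71 | 13.1-13.7% |
| Mild: week-4 SD 5 | 0.78 | 9.7-9.8% |
| Mild: week-4 SD 6 | 0.83 | 7.6-7.7% |
| Mild: week-4 SD 6.9 | 0.88 | 6.0% |
| Constant | 0.92 | 5.0% |

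**With placebo-based imputation.** Trials were simulated under no effect: 200 versus 100, 12 visits, monotone dropout, sequential placebo-regression imputation, 20 data sets, Rubin's rules. Set-up A used integer-rounded scores and 1,100-1,500 trials per setting. Set-up B used 1,000 trials per setting and Barnard-Rubin degrees of freedom. Monte Carlo SE was at most 1.2 points.

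| Imputed | AR(1), strong | AR(1), mild | AR(1), constant | Unstructured |
|---|---|---|---|---|
| 10% (A) | 10.8-17.0% | 5.9-9.5% | not run | 4.4-5.0% |
| 12% (B) | 10.0-14.0% | 5.3-5.8% | 3.8% | 2.4-4.1% |
| 20% (A) | 7.2-13.1% | 3.1-5.5% | not run | 2.3-2.9% |
| 10% plus 12% deaths (B) | 18.6% | 7.0% | 5.0% | 2.0-4.9% |
| 35% (B) | 5.4-11.9% | about 2% | 0.8% | 0.8-2.0% |

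Deaths were set near the worst 5th percentile of the visit, which is one reading of the composite rule in SAP 5.2. The simulations of set-up B omit covariates and take dropout as completely at random.

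The unstructured fit is never inflated, so the inflation comes from the fallback. All figures fall as more is imputed, because this imputation with Rubin pooling is itself conservative.

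**The case against.** The strongest objection is that the rule will hardly ever be used. The model is fitted after imputation, with about 300 patients for 78 covariance parameters. Unstructured fits by iterated generalised least squares to 5,000 simulated complete 12-visit data sets, under five covariance settings, gave no failures. That is not PROC MIXED, and some intermittent gaps could remain in the real data, but it supports calling the fallback unlikely. This part of the objection stands and is why the point is minor.

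Second, the size rests on variance growth that nobody has seen. This also stands. A reader might take 3.4 and 6.9 as early and late SDs; Protocol 11.2 does not say that. The direction follows from the structures named; the percentages are conditional.

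Third, the code is only an example, so the complaint might be reduced to an unstated SE method. This stands only in part. The named structures are a stated rule, and nothing in the SAP departs from model-based standard errors.

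A reader might also infer that the trial's type I error is 12-19%, or multiply those figures by a guessed chance of non-convergence to obtain an overall rate. The documents support neither. The figures apply only if the fallback is used, and the documents give no probability for that.

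**Conclusion.** The point holds as a minor one. If the unstructured model does not converge, the stated fallback gives too small a standard error at week 48 whenever the variance of change from baseline grows, and the confirmatory test is then too liberal.

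The size is conditional on the assumed growth. With complete data, AR(1) gives about 12-19% under strong growth, about 6-10% under mild growth (week-4 SD 5 to 6.9) and 5.0% under constant variance. With 10-20% imputed by the placebo-based method, simulations gave about 7-19% for strong growth and about 3-10% for mild growth. The upper end for strong growth is the setting with a further 12% of deaths imputed at a poor value. Heavier missingness gave lower values.

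Nothing changes if the unstructured model converges, which is the likely outcome.

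**What to change.** Add one clause to SAP 5.6.1 before unblinding: if any covariance structure other than unstructured is used, standard errors will be empirical (sandwich), with a compatible degrees-of-freedom method, for example ddfm=bw in place of ddfm=kr.

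In set-up A, sandwich standard errors with the fallback gave 4.4-4.9% at 10% imputed and 2.3-2.9% at 20% imputed, within 0.1 point of the unstructured fit. Heterogeneous-variance structures may be added but are not sufficient alone: a heterogeneous AR(1) still gave 8-14% under strong growth. Stating that one structure will be used across all 20 imputed data sets is an optional clarification.

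The cost is the EMPIRICAL option and a changed DDFM= option in the program, and only if a fallback is needed. The interval would then be wider than under the current fallback: with complete data, an SE of about 0.92 instead of 0.62-0.88, depending on growth. No additional patients or data are needed.
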